3.1.1.3 Imaging

All imaging will be sent to the central imaging core laboratory for independent review as soon as possible within 48 hours of acquisition. Further instructions will be provided by the imaging core laboratory in separate guidelines.

Patients will undergo 4 types of imaging during the dose escalation phase: planar whole body (WB) scans, single photon emission computed tomography (SPECT)/CT scans, diagnostic CT scans, and brain MRI scans, as shown in [Table 1](#). Imaging to evaluate the organ/target lesion uptake will be performed after each CAM-H2 administration during the dose escalation phase of

the study for all patients at all dose levels. Dosimetry in tumor lesions, calculated based on consecutive SPECT/CT and planar WB scans, will be performed during Cycle 1. To evaluate disease progression, diagnostic CT scans will be performed in all patients, and brain MRI will only be performed in patients with known brain metastases. Patients with extracranial lesions will be evaluated for progression using RECIST version 1.1. Patients with brain metastases without extracranial lesions will be evaluated for progression using RANO-BM. Patients with extracranial lesions and brain metastases will be evaluated for progression using both RECIST version 1.1 (extracranial lesions) and RANO-BM (brain metastases). Additional details are provided in the Imaging Review Charter.

Table 1. Imaging During the Dose Escalation Phase

Type of Imaging	Cycle 1	Cycles 2, 3, and 4
Planar WB scans for PD distribution [1], evaluation of organ/target lesion uptake, and/or dosimetry	
After each dose (Dose 1 and Dose 2):
 
 • 5 hours (± 1 hour) after CAM-H2 [2]; • 24 hours (± 4 hours) after CAM-H2; • 48 hours (± 4 hours) after CAM-H2; and • 168 hours (± 24 hours) after CAM-H2. 	After each dose (Dose 1 and Dose 2): • 24 hours (± 4 hours) after CAM-H2 [2].
SPECT/CT scans to evaluate organ/target lesion uptake and/or dosimetry	
After each dose (Dose 1 and Dose 2):
 
 • 5 hours (± 1 hour) after CAM-H2; • 24 hours (± 4 hours) after CAM-H2; • 48 hours (± 4 hours) after CAM-H2; and • 168 hours (± 24 hours) after CAM-H2. 	NA

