3.1.2.3 Imaging

As in the dose escalation phase, all imaging will be sent to the central imaging core laboratory for independent review as soon as possible within 48 hours of acquisition. Further instructions will be provided by the imaging core laboratory in separate guidelines.

Patients in the dose expansion phase will undergo planar WB scans, SPECT/CT scans, diagnostic CT scans, and brain MRIs, as shown in [Table 2](#). As in the dose escalation phase, imaging to evaluate the organ/target lesion uptake will be performed after each CAM-H2 administration; however, it will be performed less frequently. Imaging to evaluate disease progression will be performed as done in the dose escalation phase (see [Section 3.1.1.3](#)).

Table 2. Imaging During the Dose Expansion Phase

Type of Imaging	Cycle 1	Cycle 2
Planar WB scans for PD distribution and evaluation of organ/target lesion uptake	After each dose (Dose 1 and Dose 2): • 24 hours (\pm 4 hours) after CAM-H2 [1].	After each dose (Dose 1 and Dose 2): • 24 hours (\pm 4 hours) after CAM-H2 [1].
SPECT/CT scans to evaluate organ/target lesion uptake	After each dose (Dose 1 and Dose 2): • 24 hours (\pm 4 hours) after CAM-H2.	NA
Diagnostic CT scans to evaluate disease status	At screening and after Dose 2 only [2]: • 4 weeks after CAM-H2 at Visit 10 (Week 8); and • Every 8 weeks after Visit 10 (Week 8), as long as the patient had clinical benefit after Cycle 1 [3] and there is no disease progression.	After Dose 2 only [2]: • 4 weeks after CAM-H2 at Visit 19 (Week 8); • At Visit 20 (Week 11/EOT); and • Every 8 weeks after Visit 20 (Week 11), as long as there is no disease progression.
Brain MRI scans to evaluate disease status [4]	At screening and after Dose 2 only [2]: • 4 weeks after CAM-H2 at Visit 10 (Week 8); and • Every 8 weeks after Visit 10 (Week 8), as long as the patient had clinical benefit after Cycle 1 [3] and there is no disease progression.	After Dose 2 only [2]: • 4 weeks after CAM-H2 at Visit 19 (Week 8); • At Visit 20 (Week 11/EOT); and • Every 8 weeks after Visit 20 (Week 1), as long as there is no disease progression.

1. During Dose 1 of the cycle, the first planar WB scan will also serve as the PD distribution scan.

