3.1.3 Long-Term Follow-Up Period

A long-term follow-up period will start after the EOT/Early Termination (ET) Visit. Follow-up will continue for a maximum of 12 months. All patients without disease progression will be monitored every 8 weeks to evaluate PFS for a maximum of 12 months or until disease progression, death, or consent is withdrawn, whichever occurs first.

The bi-monthly visits will consist of imaging to evaluate disease status, performance status evaluation using the Eastern Cooperative Oncology Group performance status (ECOG PS), and assessment for any post-investigational treatment. Other changes in medical history or concomitant medications and AEs will be assessed. Imaging to evaluate disease status will begin 8 weeks after the last diagnostic CT scan or brain MRI performed during the study treatment period. Diagnostic CT scan will be performed in all patients. Brain MRI will only be performed in patients with known brain metastases. Patients with extracranial lesions will be evaluated for progression using RECIST version 1.1. Patients with brain metastases without extracranial lesions will be evaluated for progression using RANO-BM. Patients with extracranial lesions and brain metastases will be evaluated for progression using both RECIST version 1.1 (extracranial lesions) and RANO-BM (brain metastases). Additional details are provided in the Imaging Review Charter.

As long as there is no disease progression, imaging to evaluate disease status will be performed every 8 weeks.

For patients with disease progression or starting alternative anticancer therapy, imaging to evaluate disease status will be performed according to the local site standard of care. Review of images at this point will be done locally and not by the central imaging core laboratory. Additionally, those patients will no longer be followed every 8 weeks, but every 12 weeks, to assess survival, disease status, and post-progression therapy. Follow-up contacts (by clinic visits or telephone call) will be performed every 12 weeks until death, lost to follow-up, study end (12 months post-last patient EOT/ET Visit), or study termination by the Sponsor, whichever occurs first.

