7 EFFICACY AND DOSIMETRY VARIABLES

7.1 Primary Efficacy Variables

The primary efficacy endpoints are as follows:

- Proportion of patients achieving an objective response (CR or PR) with the use of CAM-H2 as measured by RECIST version 1.1 (all patients with extracranial lesions) or as measured by RANO-BM (patients with brain metastases without extracranial lesions); and
- CBR of CAM-H2 using the equation $CBR = CR + PR + SD$, as measured by RECIST version 1.1 (all patients with extracranial lesions) or as measured by RANO-BM (patients with brain metastases without extracranial lesions).

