7.4 Efficacy Assessments

7.4.1 Objective Response

The proportion of patients achieving an objective response will be measured using RECIST version 1.1 (see [Appendix D](#)) or RANO-BM (see [Appendix E](#)). All patients with extracranial lesions will be evaluated for progression using RECIST version 1.1. Patients without extracranial lesions will be evaluated for progression using RANO-BM.

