Disease response in target and non-target lesions will be assessed by the Investigator using RECIST version 1.1, according to the categories and criteria described in [Table 12](#) below.

Table 12. Response Evaluation Criteria in Solid Tumors Version 1.1 Guidelines

Disease Response Criteria for Target and Non-Target Lesions	
Evaluation of Target Lesions	
CR	Disappearance of all target lesions. Any pathologic lymph nodes (whether target or non-target lesions) must have a reduction in SAD to less than 10 mm.
PR	At least a 30% decrease in the SOD (LD for non-nodal lesions and SAD for nodal lesions) of target lesions, taking as reference the baseline sum diameters.
SD	Neither sufficient shrinkage to qualify for PR nor sufficient increase to qualify for PD, taking as reference the smallest sum diameters since the treatment started.
PD	At least 20% increase in the sum of the diameters of target lesions, taking as reference the smallest sum on study (this includes the baseline sum if that is the smallest sum on study). In addition to the relative increase of 20%, the sum must also demonstrate an absolute increase of at least 5 mm (Note: the appearance of 1 or more new lesions is also considered progression).
Evaluation of Non-Target Lesions	
CR	Disappearance of all non-target lesions and normalization of tumor marker level.
Non-CR/Non-PD	Persistence of 1 or more non-target lesion(s) or/and maintenance of tumor marker level above the normal limits.
PD	Appearance of 1 or more new lesions and/or unequivocal progression of existing non-target lesions.

CR = complete response; LD = longest diameter; PD = progressive disease; PR = partial response; SAD = short axis diameters; SD = stable disease; SOD = sum of the diameters.

Source: Eisenhauer EA, Therasse P, Bogaerts J, et al. New response evaluation criteria in solid tumours: revised RECIST guideline (version 1.1). *Eur J Cancer*. 2009;45(2):228-247

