- Non-target: All other lesions not classified as target lesions are to be identified as non-target lesions. Non-target lesions should be identified and recorded in the electronic case report form at baseline. Measurement is not required.

Disease response in target and non-target lesions will be assessed by the Investigator using RANO-BM, according to the categories and criteria described in [Table 13](#) and [Table 14](#) below.

Table 13. Response Assessment in Neuro-Oncology Brain Metastases

Disease Response Criteria for Target and Non-Target Lesions	
Evaluation of Target Lesions	
CR	Disappearance of all CNS target lesions sustained for at least 4 weeks with no new lesions, no use of corticosteroids, and patient is stable or improved clinically.
PR	At least a 30% decrease in the sum longest diameter of CNS target lesions, taking as reference the baseline sum longest diameter sustained for at least 4 weeks; no new lesions; stable to decreased corticosteroid dose; stable or improved clinically.
SD	Neither sufficient shrinkage to qualify for PR nor sufficient increase to qualify for PD, taking as reference the smallest sum longest diameter while on study.
PD	At least a 20% increase in the sum longest diameter of CNS target lesions, taking as reference the smallest sum on study (this includes the baseline sum if that is the smallest on study). In addition to the relative increase of 20%, at least 1 lesion must increase by an absolute value of 5 mm or more to be considered progression.
Evaluation of Non-Target Lesions	
CR	Disappearance of all enhancing CNS non-target lesions and no new CNS lesions.
Non-CR or Non-PD	Persistence of 1 or more non-target CNS lesion or lesions.
PD	Unequivocal progression of existing enhancing non-target CNS lesions, new lesion(s) (except while on immunotherapy-based treatment*), or unequivocal progression of existing tumor-related non-enhancing (T2/FLAIR) CNS lesions.

*In the case of immunotherapy-based treatment, new lesions alone may not constitute PD.
CNS = central nervous system; CR = complete response; PD = progressive disease; PR = partial response; SD = stable disease; T2-FLAIR = T2-weighted fluid attenuated inversion recovery.
Source: Lin NU, Lee EQ, Aoyama H, et al. Response assessment criteria for brain metastases: proposal from the RANO group. *Lancet Oncol.* 2015;16(6):e270-e278

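### Two reads of response are planned, central and investigator, but the endpoint and interim text does not say which governs the primary ORR, CBR and the 10% termination rule

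*Combined protocol and SAP*

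**What the plan says.** **Central review.** Section 3.1.2.3 covers the expansion phase, to which the primary ORR and CBR and the interim rule belong. It states that "all imaging will be sent to the central imaging core laboratory for independent review as soon as possible within 48 hours of acquisition". Section 3.1.1.3 says the same for escalation. Sections 3.1.3 and 6.5 take the core laboratory out only after progression or the start of another anticancer therapy: "Review of images at this point will be done locally and not by the central imaging core laboratory". This implies that disease-status scans are read centrally until then.

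**Investigator assessment.** Appendix D: "Disease response in target and non-target lesions will be assessed by the Investigator using RECIST version 1.1". Appendix E: "Disease response in target and non-target lesions will be assessed by the Investigator using RANO-BM". These are the only sentences that say who assigns the response category.

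**Endpoints.** Section 7.1 defines the first primary efficacy endpoint as "Proportion of patients achieving an objective response (CR or PR) with the use of CAM-H2 as measured by RECIST version 1.1", or by RANO-BM for patients with brain metastases only. Section 7.4.1 adds "The proportion of patients achieving an objective response will be measured using RECIST version 1.1" and points to Appendix D, or to Appendix E for RANO-BM. Section 7.4.2 does the same for CBR. Section 9.2.1 lists ORR, CBR, DoR and PFS. Section 9.2.4 bases the interim on objective responses by either set of criteria and ends an indication if its ORR is below 10%. None of these sections names a reader.

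**The concern.** The plan collects an independent read, but the only text that assigns response categories gives the task to the investigator. ORR and CBR are the primary efficacy endpoints of the expansion phase. ORR also drives a hard decision, termination of an indication, and is meant to inform the power of a later Phase 2/3 study.

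Two things are at stake. Followed literally, the cross-references make the primary result an unblinded investigator assessment in an open-label study without a control arm, although an independent read of the same scans is already planned. If the cross-references are not taken as settling the matter, two results will exist with no rule for choosing between them, and the choice could be made after both are known.

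**Working it through.** No figure in the plan depends on the choice of reader, and no formal sample size calculation was done, so there is nothing to reproduce. The check is a comparison of the text, followed by an illustration of the consequence.

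**Step 1. Who reads what**

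| Place | Subject | Reader named |
|---|---|---|
| 3.1.1.3 (escalation) | All imaging | Central core laboratory |
| 3.1.2.3 (expansion) | All imaging | Central core laboratory |
| 3.1.3, 6.5 | Scans after progression or new anticancer therapy | Local only |
| 7.1 | Definition of ORR and CBR | None |
| 7.4.1, 7.4.2 | Measurement of ORR and CBR | None; refers to Appendices D and E |
| Appendices D, E | Response category | Investigator |
| 9.2.1 | Efficacy analysis | None |
| 9.2.4 | Interim ORR | None; criteria only |

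The central reviewer in Section 7.4.6 judges which lesions are avid for dosimetry, which does not settle response. No section gives a rule for disagreement between the two reads.

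**Step 2. How close the interim decision is**

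Inputs from Section 9.2.4: 52 expansion patients, an interim at about 50% of patients per indication, and a stop if the observed ORR is below 10%. The split by indication is not given, so the interim size n is assumed. An even split gives 52/2 = 26 per indication and 26/2 = 13 at the interim. If nearly all patients had one indication, n would approach 52/2 = 26. The smaller indication could fall below 13.

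An indication continues if responders x satisfy x/n ≥ 0.10, so the smallest passing count is r = ceil(0.10 n).

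- n = 5 to 10: r = 1
- n = 13 to 20: r = 2. At n = 13, 1/13 = 7.7% stops and 2/13 = 15.4% continues.
- n = 21 to 26: r = 3. At n = 26, 2/26 = 7.7% stops and 3/26 = 11.5% continues.

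At each size, one patient separates stopping from continuing.

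**Step 3. What a gap between readers would do**

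The documents give no rate of reader disagreement. Suppose the two reads had underlying ORRs of 20% and 15%, without saying which read is higher. With P(stop) = Σ C(n,x) pˣ (1−p)ⁿ⁻ˣ for x = 0 to r−1:

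- n = 13, p = 0.20: 0.80¹³ + 13 × 0.20 × 0.80¹² = 0.055 + 0.179 = 0.234
- n = 13, p = 0.15: 0.85¹³ + 13 × 0.15 × 0.85¹² = 0.121 + 0.277 = 0.398
- n = 26 (x = 0, 1, 2): 0.084 at p = 0.20 and 0.230 at p = 0.15

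Under that assumption, the choice of read moves the chance of stopping from 23% to 40% at n = 13, and from 8% to 23% at n = 26. With 20% against 10%, the figures are 23% against 62%, and 8% against 51%.

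**Step 4. What a central read would need**

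Table 13 makes a RANO-BM response depend on corticosteroid use and clinical status. Table 12 makes a RECIST non-target complete response depend on tumor markers. Scans alone do not carry these data, and the protocol describes no route for them to the core laboratory. Sections 3.1.3 and 6.5 end central review at progression without saying whose progression call counts.

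**The case against.** A reader might infer that the protocol contradicts itself. It does not, strictly: sending images for independent review and having the investigator assess response can both happen on the same scan. Only one text assigns the category, and Sections 7.4.1 and 7.4.2 lead to it, so the plan arguably does designate the investigator. On that view, asking for central review is a preference, since nothing in the documents requires it for a phase that seeks an initial estimate without a formal sample size. The Imaging Review Charter, cited for further detail, and the SAP, to which Section 9.2.4 defers the exact approach, may set the hierarchy; neither was available for this review. Finally, any cut-off at small n turns on one patient, whichever reader is named.

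Much of this stands. The two reads are compatible, the Charter or SAP may settle the point, and the one-patient margin does not itself measure reader disagreement. It does not remove the concern. If the cross-reference is decisive, the primary result rests on the unblinded read while the independent one has no stated role. If it is not, the governing read is unnamed. The endpoint and interim text does not expressly leave the choice of reader to the Charter, and a Charter making the central read primary would still have to be squared with Appendices D and E.

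**Conclusion.** The concern holds as a failure to designate. Two reads are described, and the endpoint, efficacy and interim text does not name the governing one. The literal path through Sections 7.4.1 and 7.4.2 leads to the investigator. It should be corrected before response data are seen.

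The size is conditional. For assumed interim sizes of 13 to 26, a single patient read differently can reverse the termination decision. The stopping probabilities above rest on assumed sizes and assumed reader-specific rates. The actual denominators may also differ because Section 3.1.1.2 brings escalation patients treated at the MTD or RDP2 into the efficacy readout.

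A reader might also infer that the central ORR would be lower, or that the investigator read is inflated. The documents give no data on either. The case for the central read is that it is independent and already planned, and that naming it in advance removes a post hoc choice.

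**What to change.** - **ORR, CBR and the interim ORR.** In Sections 7.4.1, 7.4.2, 9.2.1 and 9.2.4 and Appendices D and E, designate the planned central independent read as primary and the investigator read as a supportive analysis. Align Sections 3.1.1.3 and 3.1.2.3 with this.
- **DoR and PFS.** Name the governing read and state whose progression call ends central review in Sections 3.1.3 and 6.5. If an investigator call cuts off central reads for a patient whom the central reader has not called progressed, central PFS and DoR would be censored for a reason related to outcome.
- **Clinical inputs.** State how corticosteroid use, clinical status and tumor marker data reach the central assessment.
- **Clinical benefit.** Sections 3.1.1.2 and 3.1.2.2 make further cycles depend on clinical benefit without naming a reader. Those passages should be reconciled with the imaging text and the appendices. This point proposes no clinical rule.
- **Charter and SAP.** Check that both agree with the amended protocol.

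The cost is a protocol amendment, a small data-transfer step to the core laboratory and one additional supportive analysis. No extra scans are needed for ORR, CBR or the interim, because central review of all imaging is already planned.

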9.2.4 Sample Size Determination

The proposed study is a dose escalation (Phase 1) study with an expansion cohort reaching into dose expansion (Phase 2). No formal sample size calculation was performed for dose escalation (Phase 1) of the study. A maximum of 18 patients are planned for dose escalation.

No formal sample size calculation was performed for dose expansion (Phase 2). However, a planned sample size of 52 patients is deemed sufficient to obtain an initial estimate of response rates to formally power a subsequent Phase 2/3 study.

For each indication (ie, breast, gastric, or GEJ cancer), an interim evaluation of efficacy will be conducted when approximately 50% of patients complete Cycle 1 at the recommended dose for expansion based on objective responses determined from RECIST 1.1 or RANO-BM. One analysis will be performed for patients with breast cancer, and another analysis will be performed for patients with gastric or GEJ cancer. If the ORR is <10% for a specific indication (ie, breast or gastric/GEJ), the study will be terminated for that particular indication.

The Statistical Analysis Plan will provide more details on the exact statistical approach.

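### The primary ORR pools RECIST responses with no stated confirmation and RANO-BM responses that Table 13 requires to last 4 weeks, and the interim rule does not say how responses still awaiting that condition count

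*Combined protocol and SAP*

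**What the plan says.** Section 7.1 defines the primary objective response as one proportion, with the criterion chosen by lesion site: "as measured by RECIST version 1.1 (all patients with extracranial lesions) or as measured by RANO-BM (patients with brain metastases without extracranial lesions").

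The two criteria are printed in the appendices:

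- **RECIST 1.1 (Appendix D, Table 12).** CR is "Disappearance of all target lesions. Any pathologic lymph nodes (whether target or non-target lesions) must have a reduction in SAD to less than 10 mm". A partial response is "At least a 30% decrease in the SOD (LD for non-nodal lesions and SAD for nodal lesions) of target lesions", relative to baseline. Neither carries a duration or confirmation condition.
- **RANO-BM (Appendix E, Table 13).** CR is "Disappearance of all CNS target lesions sustained for at least 4 weeks with no new lesions". PR is a 30% decrease, "taking as reference the baseline sum longest diameter sustained for at least 4 weeks". Appendix E directs the assessor to both Table 13 and Table 14, and Table 14 has no 4-week condition.

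No section requires confirmation for the ORR. Section 9.2.1 applies the word confirmed to response only for the descriptive near-CR category.

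Section 9.2.4 places the interim "when approximately 50% of patients complete Cycle 1 at the recommended dose for expansion", separately for breast and for gastric/GEJ cancer. The consequence is: "If the ORR is <10% for a specific indication (ie, breast or gastric/GEJ), the study will be terminated for that particular indication". It gives no data cut-off, no minimum follow-up, and no rule for a response still awaiting the 4-week condition.

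**The concern.** Consider two patients with the same 30% shrinkage on the same single scan. On the printed text, the one with extracranial disease is a responder. The one with brain-only disease is not, until the shrinkage has lasted 4 weeks. A proportion built this way has no single meaning.

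The expansion is single-arm, so no control group absorbs measurement error around the 30% threshold. Section 9.2.4 intends the estimate to support the powering of a later study, so any upward error would carry into that design. The same ORR also drives a termination rule, and that rule is read at a time when some patients have had only one disease scan after baseline.

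**Working it through.** **1. What the plan's own figure allows.** The planned 52 patients cannot be reproduced. Section 9.2.4 says no formal calculation was made and gives no null rate, target rate or precision goal. There is therefore no stated error rate against which to measure a bias.

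**2. Direction.** Every confirmed response is also a single-scan response, so unconfirmed ORR ≥ confirmed ORR. This needs no assumption.

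**3. Size, as an illustration only.** The documents give no non-confirmation rate. Assume 16 responders in 52 and a loss of 10% or 25%: 16 × 0.90 = 14.4, taken as 14; 16 × 0.75 = 12. Exact (Clopper-Pearson) 95% intervals:

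| Responders | ORR | 95% CI |
|---|---|---|
| 16/52 | 31% | 19% to 45% |
| 14/52 | 27% | 16% to 41% |
| 12/52 | 23% | 13% to 37% |

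The loss is applied to all 16. Any brain-only responder counted under Table 13 has already met the 4-week condition, so the shift would be smaller if some of the 16 were brain-only.

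**4. Scans available when a patient completes Cycle 1.**

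- The first disease scan after baseline is at Week 8 (Table 2).
- For a patient continuing to Cycle 2, Week 11 imaging is not done (Section 6.3.2.9).
- The next scan is at Week 8 + 8 = Week 16 by Table 2. By the Cycle 2 schedule in Table 10 it is at Cycle 2 Week 8, about Week 11 + 2 + 8 = 21.
- For a patient who has an end-of-treatment scan, Visit 10 to Visit 11 is nominally Day 50 − Day 29 = 21 days. The windows (+7 and ±7 days) allow 43 − 36 = 7 to 57 − 29 = 28 days, so 4 weeks is reached only at the extreme.

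A continuing brain-only patient at the end of his or her own Cycle 1 thus has one scan, and a 4-week response cannot yet be shown.

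**5. How many interim patients are at that point.** Assume 26 patients per indication, so 13 at the interim; the split is not given. Assume also even accrual and a data cut at the last patient's Week 12. The counts cover all patients, not only brain-only patients.

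| Accrual of the 13 | Reached Week 16 | Reached Week 21 |
|---|---|---|
| 26 weeks | 11 | 8 |
| 13 weeks | 9 | 4 |
| 8 weeks | 7 | 0 |

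**6. Effect on the stopping rule.** With n = 13, 1/13 = 7.7% stops and 2/13 = 15.4% continues, so P(stop) = (1−p)^13 + 13p(1−p)^12. At p = 0.20 this is 0.055 + 0.179 = 0.234. If b patients are pending and counted as non-responders, 13 is replaced by 13 − b (and 12 by 12 − b):

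| Pending, b | 0 | 1 | 2 | 3 |
|---|---|---|---|---|
| P(stop), ORR 20% | 0.23 | 0.27 | 0.32 | 0.38 |

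**7. Effect of requiring confirmation under an unchanged 10% rule.** With a single-scan ORR of 20%, a 10% loss gives p = 0.18 and P(stop) = 0.29. A 25% loss gives p = 0.15 and P(stop) = 0.40.

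**The case against.** **Silence is not a rule.** Table 12 lists lesion-level categories and does not define best overall response. RECIST 1.1 is adopted by reference, and detail is deferred to the Imaging Review Charter and to a SAP whose separate text is not in the supplied document. A confirmation rule could sit there. This stands as a caveat. It does not remove the point, because Appendices D and E give the operative definitions and state a duration for one criterion only.

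**The RANO-BM side is itself unsettled.** Table 14 omits the 4-week condition. A site following Table 14 alone would apply no duration rule to either criterion. This also stands, and is a reason to reconcile the two tables.

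**The interim effect may be small.** A reader might infer that no brain-only patient can count as a responder at the interim. The documents do not support that. The trigger depends on the group, so earlier enrollees are further on. Section 3.1.1.2 includes escalation patients treated at the chosen dose in the efficacy readout. If Dose 2 cannot be given, imaging starts 4 weeks after Dose 1, and a Week 11 scan would fall about 7 weeks later. In the table at step 5, nobody has reached the second scan only with fast accrual and the Table 10 timing. The 10 to 12 breast patients in Section 3.1.2.1 have measurable brain metastases, not necessarily brain-only disease.

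**The illustrated shift is modest.** It is 2 to 4 patients, with widely overlapping intervals, in a study that states no formal test. That is fair. The objection to mixed definitions does not depend on the size of the shift.

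**Conclusion.** The point holds in this form: the printed criteria apply different persistence requirements to patients pooled in one primary proportion, and the RECIST part, as printed, can only equal or exceed a confirmed rate. A reader might go further and infer a known inflation of the ORR. The documents give no rate from which to derive one; the fall from 31% to 27% or 23% rests on an assumed 10% to 25% loss and an assumed 16 responders.

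At the interim the gap is limited to brain-only patients who have just finished Cycle 1 and are continuing. Their responses are pending, and the plan does not say how pending responses count. With an assumed 13 patients and a true ORR of 20%, counting one to three such patients as non-responders would raise the chance of stopping from 0.23 to between 0.27 and 0.38. How many there would be is not known. The definition should be settled before results are seen, because it governs both a primary endpoint and a termination rule.

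**What to change.** - Define the primary ORR as confirmed response under both RECIST 1.1 and RANO-BM, with the two assessments at least 4 weeks apart and the next scheduled disease scan used as the confirming one. Report unconfirmed ORR as supportive.
- Reconcile Table 13 with Table 14 on the 4-week condition.
- Reconcile Table 2 (about Week 16) with Table 10 (about Week 21) on the next scan for patients continuing to Cycle 2.
- For the 10% rule, use one response definition for both criteria. Either count single-scan responses for both, or cut the data only after first-scan responders have had their confirming scan, so that pending responses are not read as non-responses.

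The changes are to wording and use scans already scheduled. The reported ORR will be somewhat lower. Waiting for confirmation makes the interim later and, with the 10% threshold unchanged, more likely to stop (0.23 to between 0.29 and 0.40 in the example at step 7). Using single-scan responses avoids that, but rests the interim decision on unconfirmed data. The sponsor should choose between these openly and record the choice.
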